**Clinical Study Protocol**  
**Johnson & Johnson Vision Care, Inc.**

| ARM 2                           |                          |   |            |
|--|--------------------------|---|------------|
| Visit 3: Treatment 2, 2-Week Follow-Up |                          |   |            |
| Step                                   | Procedure                | Details   | [REDACTED] |
|  |                          | NOTE: if lens fit is unacceptable subject will be discontinued from the study.                         |            |
| 3.10.                                  | Lens Removal and Discard | The lenses will be removed by the subject and discarded.

Proceed to Final Evaluation (Step F.1) | N/A        |

**FINAL EVALUATION (ARM 1 & ARM 2)**

The final evaluation will ordinarily take place immediately following the last scheduled follow-up visit per the study protocol. It may also take place at any point the subject discontinues the study or is terminated from the study.

| Final Evaluation |                              |   |                          |
|------------------|------------------------------|---|--------------------------|
| Step             | Procedure                    | Details   | [REDACTED]               |
| F.1              | Final Exam Form              | Indicate if the subject completed the study successfully. If subject discontinued from the study, indicate the reason.  |                          |
| F.2              | Exit Refraction              | Perform bare-eye subjective spherocylindrical refraction with a phoropter and record the best-corrected distance visual acuity (OD and OS) to the nearest letter.

Note: This step is not necessary if the subject was exited due to screen failure.   | [REDACTED]
[REDACTED] |
| F.3              | Exit Slit Lamp Biomicroscopy | FDA Slit Lamp Classification Scale will be used to grade the findings.

If the clearance of the fluorescein needs to be expedited, preservative-free rewetting drops or saline may be instilled. This step is not necessary if the subject was exited due to screen failure.

Note: This step is not necessary if the subject was exited due to screen failure, or if biomicroscopy was performed as part of the final follow-up visit procedures (i.e., immediately prior to the final evaluation). | [REDACTED]               |

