**ARM 1 STUDY PROCEDURES**

**VISIT 2 (14 ± 2 days following Visit 1)**

**Subjects must present with study lenses on eye for at least 2 hours.**

| ARM 1              |   |  |     |
|---------------------------|---|--|-----|
| Visit 2: 2-Week Follow-Up |   |  |     |
| Step                      | Procedure   | Details  |     |
| 2.1.                      | Adverse Events and Concomitant Medications Review | Review any changes to the subject's medical history or concomitant medications from the previous study visit. Record any changes, and any adverse events.                                      | N/A |
| 2.2.                      | Wear time   | Record the average wear time and comfortable wear time.  | N/A |
| 2.3.                      | Compliance  | Confirm compliance with the prescribed wear schedule.  | N/A |
| 2.4.                      | Subject Reported Ocular Symptoms                  | Subjects will respond to a verbal open-ended symptoms questionnaire.   |     |
| 2.5.                      | CLDEQ-8 Questionnaire                             | The subject will respond to the CLDEQ-8 Questionnaire (Appendix A)   |     |
| 2.6.                      | Follow-up questionnaires                          | The subject will respond to the CLUE and MRD Follow Up Questionnaire (Appendix A)  |     |
| 2.7.                      | Entrance Visual Acuity                            | Record the distance Snellen visual acuity with the contact lenses (OD, OS) to the nearest letter. Subjects must read the smallest line until at least 50% of the letters are read incorrectly. |     |

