**Clinical Study Protocol**  
**Johnson & Johnson Vision Care, Inc.**

| ARM 2  |                                |  |
|---|--------------------------------|--|
| Visit 2: Treatment 1, 2-Week Follow-Up; Treatment 2 Fitting |                                |  |
| Step  | Procedure                      | Details  |
| 2.5.  | CLDEQ-8 Questionnaire          | 
The subject will respond to the CLDEQ-8 Questionnaire (Appendix A).
 
NOTE: If subjects no longer meet score criteria of <math>\geq 15</math>, the lenses will be removed by the subject and discarded. The subject will be discontinued and proceed to final evaluation (F.1)
   |
| 2.6.  | Follow Up questionnaires       | 
The subject will respond to the CLUE and MRD Follow Up Questionnaire (Appendix A)
   |
| 2.7.  | Entrance Visual Acuity         | 
Record the distance Snellen visual acuity with the contact lenses (OD, OS) to the nearest letter. Subjects must read the smallest line until at least 50% of the letters are read incorrectly.
  |
| 2.8.  | Subjective Lens Fit Assessment | 
Evaluate overall lens fit acceptance (acceptable or unacceptable) based on centration, movement and other fitting characteristics.
 
An unacceptable fit is deemed by one of the following criteria:
 
 
• limbal exposure at primary gaze or with extreme eye movement.
 
• edge lift.
 
• excessive movement in primary and up gaze.
 
• insufficient movement in all three of the following conditions: primary gaze, up gaze, and Josephson push up.
 
 
NOTE: if lens fit is unacceptable subject will be discontinued from the study.
 |
| 2.9.  | Lens Removal and Discard       | 
The lenses will be removed by the subject and discarded.
  |

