# **Clinical Study Protocol**

## **Johnson & Johnson Vision Care, Inc.**

- Subject not successfully dispensed due to lack of efficacy and safety including poor vision, poor comfort or unacceptable fit.

For discontinued subjects, the Investigator will:

- Complete the current visit (scheduled or unscheduled).
- Complete the Final Evaluation, indicating the reason that the subject was discontinued from the study.
- Record the spherocylindrical refraction with best corrected distance visual acuity.
- Collect used test article(s) (worn or brought to the visit) from the subject and discard them, unless otherwise stated in Section 7.2.
- Collect all unused test article(s) from the subject.
- Make arrangements for subject care, if needed, due to their study participation

An additional subject will be enrolled if a subject discontinues from the study prematurely.

In cases where a subject is lost to follow-up, every possible effort must be made to contact the subject and determine the reason for discontinuation/withdrawal. The measures taken to follow up must be documented including two written attempts and a certified letter (or equivalent) as the final attempt

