## **14. STATISTICAL METHODS**

### **14.1. General Considerations**

Statistical Analysis will be undertaken by the sponsor or under the authority of the sponsor. A general description of the statistical methods to be implemented in this clinical trial is outlined below. More details will be included in the stand-alone Statistical Analysis Plan (SAP). The SAP will be developed and finalized prior to database lock.

All data summaries and statistical analyses will be performed using the SAS software Version 9.4 or higher (SAS Institute, Cary, NC). Throughout the analysis of data, the results for each subject/eye will be used when available for summarization and statistical analysis. Unscheduled visits will be summarized separately and will be excluded from the statistical analysis.

Summary tables (descriptive statistics and/or frequency tables) will be provided for all baseline variables, efficacy variables and safety variables as appropriate. Continuous variables will be summarized with descriptive statistics (n, mean, standard deviation (SD), median, minimum and maximum) and will be summarized by lens type and ARM (ARM1- AO1D and ARM2 – Subjects' Habitual Lenses and AO1D) Frequency count and percentage of subjects or eyes within each category will be provided for categorical data.

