#### **Intent-to-Treat (ITT) Population:**

All randomized subjects regardless of actual treatment and subsequent withdrawal from the study or deviation from the protocol. At least one observation should be recorded.

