### **Hypothesis Testing:**

The null and alternative hypotheses for non-inferiority of the Test relative to Control are as follows:

$$H_0: \Delta \leq -5$$

$$H_A: \Delta > -5,$$

where  $\Delta$  is the difference between lens types (Test minus Control) in mean change from baseline at 2-week follow-up. Non-inferiority of the Test lens relative to the Control lens will be based on the LSM difference in the score change from baseline at 2-week follow-up and its corresponding 95% confidence interval from the final model. The lower bound of the 95% CI will be compared to the non-inferiority margin of -5. If the lower bound is greater than -5, the null hypothesis will be rejected, and the Test lens will be considered non-inferior to the Control lens. If non-inferiority of the Test lens over Control lens is met, then superiority test will be also conducted on the ITT population. If the lower bound is greater than 0, then the superiority of the Test lens over the Control lens will be established

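### Subjects who leave before the Visit 2 questionnaires have no post-baseline CLUE or CLDEQ-8, and ARM 2 Step 2.5 can skip CLUE for improved controls; both weaken the ITT superiority and sensitivity analyses

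*Combined protocol and SAP*

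**What the plan says.** **Exit procedures.** For a discontinued subject, Section 8.2 tells the investigator to do two things that matter here: "Complete the current visit (scheduled or unscheduled") and "Complete the Final Evaluation, indicating the reason that the subject was discontinued from the study". Section 7.2 adds, on timing, "It may also take place at any point the subject discontinues the study or is terminated from the study". The Final Evaluation has three steps: F.1 (exam form), F.2 (refraction) and F.3 (slit lamp). Steps U.1 to U.8 of Section 7.3 contain no questionnaire, and Section 14.1 states: "Unscheduled visits will be summarized separately and will be excluded from the statistical analysis".

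**Where the endpoint is collected.** In ARM 1 the only post-baseline CLUE is at Visit 2, Step 2.6 ("The subject will respond to the CLUE and MRD Follow Up Questionnaire (Appendix A")), with CLDEQ-8 at Step 2.5. In ARM 2 both come at Visit 2 and again at Visit 3. At ARM 2 Visit 2, a subject who scores below 15 at Step 2.5 takes another route: "The subject will be discontinued and proceed to final evaluation (F.1"). CLUE follows only at Step 2.6.

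**Analysis.** Section 14.3 defines ITT as "All randomized subjects regardless of actual treatment and subsequent withdrawal from the study or deviation from the protocol". Section 14.5 tests non-inferiority on the per-protocol (PP) set, uses ITT for a sensitivity analysis, and continues: "If non-inferiority of the Test lens over Control lens is met, then superiority test will be also conducted on the ITT population". Section 14.9 imputes nothing in the main analysis. It adds multiple imputation as a sensitivity analysis only when dropout exceeds 15%.

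**The concern.** The ITT set keeps leavers by name, but the visit schedule gives no follow-up score for those who stop before the Visit 2 questionnaires. They enter the mixed model with a baseline value and no observed change, so the estimated change contrast rests on subjects who reached the questionnaires.

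That is harmless only if leaving is unrelated to comfort once the modelled variables are taken into account. Two mechanisms could break this, and both would plausibly favour AO1D:

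- **ARM 1.** Section 8.2 withdraws subjects for adverse events that stop lens wear, for corneal infiltrative events and for non-compliance with the wear schedule. A new lens may produce more such exits in two weeks than a lens the subject already wears.
- **ARM 2.** Taken in the order written, Step 2.5 removes CLUE from control subjects whose dryness score has improved. ARM 1 has no such step.

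Scores that were never asked for cannot be recovered at analysis.

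**Working it through.** **1. The plan's own figures.** With the SDs in Section 14.2 (25.21 and 18.12), a true difference of 9 and the margin of 5, the distance to the margin is 14. A Satterthwaite t-test at two-sided 0.05 then needs 40 per arm (power 80.3%), as Table 9 states. The total follows as 80 × 1.4 = 112. The text's 24% figure is (42 + 23)/265 = 65/265 = 0.245. It mixes screen failures with discontinuations, so it is not the rate needed here.

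**2. The relevant rate.** From Table 10, discontinued divided by dispensed:

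| Study | Discontinued/dispensed | Rate |
|---|---|---|
| First | 8/81 | 9.9% |
| Second | 10/49 | 20.4% |
| Third | 5/92 | 5.4% |
| Pooled | 23/222 | 10.4% |

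At the pooled rate, 40 × 0.104 = 4.1 subjects per arm would leave after dispensing. These are upper bounds for this point, because they cover all causes and not every exit need precede the first follow-up questionnaire.

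**3. Illustrative bias from ARM 1 losses.** Let p be the share of ARM 1 without a follow-up CLUE and d the gap in mean change between stayers and leavers. The full mean is (1 − p)·stayers + p·leavers, so the observed mean is too high by p × d. The documents give no d. Assume d = 20 (borrowed from the population SD of CLUE scores in Section 2.2, which is not evidence about leavers), similar baselines, and no comparable loss in ARM 2:

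| p | p × 20 | If half leave for discomfort |
|---|---|---|
| 0.054 | 1.1 | 0.5 |
| 0.104 | 2.1 | 1.0 |
| 0.204 | 4.1 | 2.0 |

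Varying d instead: if the observed difference is 9 and leavers' true difference from control lies between 0 and −20, d runs from 9 to 29. At p = 0.104 the overstatement is 0.93 to 3.0 points; for p between 0.05 and 0.15 it is 0.45 to 4.35.

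For scale, the standard error of the contrast at 40 per arm is √((25.21² + 18.12²)/40) = √24.10 = 4.9. The pooled illustration of 2.1 points is therefore about 0.4 standard errors. Power for superiority at a true difference of 9 is 44%.

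**4. Would the imputation trigger help?** At 10.4% dropout it does not fire. In the ARM 1-only scenario at 20.4%, dropout over two equal arms is 20.4/2 = 10.2%, again below 15% if the trigger is read trial-wide. At 20.4% across the trial it would fire. Regression-based imputation from the observed data would still not correct loss that depends on the unobserved score.

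**5. The ARM 2 Step 2.5 exit.** The documents do not say how many controls will score below 15. As an illustration, take baseline mean 20.3 and SD 4.39 (Table 7), change SD 5.0 (Section 14.2), normal scores, and change independent of baseline. The Visit 2 SD is √(4.39² + 5.0²) = 6.65. With zero mean change, the share below 15 is Φ((15 − 20.3)/6.65) = Φ(−0.80) = 21%, or 8 to 9 of 40. A mean change of 2 points either way gives 14% (worsening) to 31% (improvement). How far this would shift the CLUE contrast depends on the relation between CLDEQ-8 and CLUE changes, which the documents do not report, so no bias is computed.

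**The case against.** **The primary decision is untouched.** Non-inferiority is decided on PP, which requires all visits to be completed (Section 14.3), and Section 2.3 states no superiority hypothesis for the primary endpoint. This stands. A reader might set these biases beside the 5-point margin, but early leavers and Step 2.5 exits are outside PP whether or not they answer the questionnaires.

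**Informative loss is not shown.** A reader might cite poor comfort in Section 8.2 as proof. That item concerns subjects who were not successfully dispensed, so it does not describe discomfort during wear. Section 14.9 says past trials give no evidence of systematic dropout. The model also takes baseline as a response, so baseline-only subjects stay in the likelihood under missing-at-random. This stands against any claim that bias towards AO1D is established. The adverse-event and compliance reasons make it plausible, no more.

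**Some exits may be covered.** Section 7.2 says the Final Evaluation may occur at exit, and subjects lost to follow-up will not attend, so it would be wrong to infer that every leaver is seen. A subject stopped during Visit 2 is covered if Section 8.2 is followed. Section 7.3 asks for final-visit forms on withdrawal, and Table 3 labels ARM 1 Visit 2 as including the Final Evaluation. That could be read as bringing the questionnaires along, but Section 7.3 ties those forms to recording the reason for withdrawal, and F.1 to F.3 list no questionnaire. The COVID-19 guidance in Appendix E allows key efficacy assessments only as feasible, and its remote-visit table lists neither instrument.

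**Early scores are not 2-week scores.** This is correct, and it is why they belong in a sensitivity analysis.

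**Conclusion.** The gap holds on the text. Dispensed subjects who leave before the Visit 2 questionnaires have no scheduled post-baseline CLUE or CLDEQ-8, and Step 2.5 conflicts with Section 8.2 on whether CLUE is collected from ARM 2 subjects scoring below 15. What is weakened is the ITT superiority test and the ITT sensitivity analysis. Replacing leavers (Sections 4.3 and 8.2) restores the number of completers but not the missing scores.

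Both mechanisms would plausibly favour AO1D, but neither direction nor size is established. The range of about 1.1 to 4.1 points (2.1 pooled), or half that if half leave for discomfort, is an upper-end illustration. It rests on an assumed 20-point gap, all-cause rates from studies whose identity is redacted, and losses in ARM 1 only. The Step 2.5 component is not quantified in CLUE points.

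The change is worth making because it is cheap and has to be in place before data collection.

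**What to change.** 1. **ARM 2 Visit 2.** Reconcile Step 2.5 with Section 8.2 so that the questionnaires at Steps 2.5 and 2.6 are both completed before any subject goes to F.1. The discontinuation rule itself is left as it is. State that these Visit 2 scores enter the ITT analysis.
2. **Final Evaluation.** For any dispensed subject who attends and exits before the Visit 2 questionnaires, add CLDEQ-8 and the CLUE/MRD follow-up form, answered about the lens last worn, with the exit day recorded. Say in the SAP that these early scores are used in a pre-specified ITT sensitivity analysis and not in PP. Exempt them from the Section 14.1 exclusion of unscheduled-visit data for that analysis.

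**Cost.** Protocol wording, one conditional eCRF form and about 10 minutes at a visit the subject already attends. Some scores will precede two weeks of wear, and the CLDEQ-8 two-week recall will then cover the study lens only in part. Appendix A is not reproduced in the text reviewed, so the form's wording should be checked for early use. Subjects lost to follow-up remain uncaptured.

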# Clinical Study Protocol

## Johnson & Johnson Vision Care, Inc.

### 7.3. Unscheduled Visits

If, during the investigation, a subject requires an unscheduled visit to the clinical site, the following information will be collected, as appropriate:

- Chief complaint prompting the visit. If the reason is an adverse event, the applicable eCRF for the adverse event must be completed and subject record completed as appropriate.
- Date and time of the visit and all procedures completed at the unscheduled visit.
- Review of adverse event and concomitant medications.
- Documentation of any test article dispensed or collected from the subject, if applicable.
- Slit lamp findings (using the Slit Lamp Classification Scale).

If the Investigator withdraws a subject from the study, the final study visit case report forms must be completed indicating the reason(s) why the subject was withdrawn. The subject record must be completed documenting the date and primary reason for withdrawal and the study CRA notified.

Any ocular and non-ocular Adverse Events that are ongoing at the time of the study visit will be followed by the Investigator, within licensure, until they have resolved, returned to pre-treatment status, stabilized, or been satisfactorily explained. If further treatment i.e., beyond licensure is required, the subject will be referred to the appropriate health care provider.

The following information will be collected during an unscheduled visit.

| Unscheduled Visit |   |   |
|-------------------|---|---|
| Step              | Procedure   | Details   |
| U.1               | Reason for unscheduled visit                                      | Indicate if the only reason for the visit is that the subject requires additional test articles. If the reason is other than resupply of previously dispensed lenses, specify the reason for the visit.  |
| U.2               | Chief Complaints (if applicable)                                  | Record the subject's chief complaints for reasons for the unscheduled visit.  |
| U.3               | Adverse Events and Concomitant Medications Review (if applicable) | Review any changes to the subject's medical history or concomitant medications from the previous study visit. Record any changes, and any adverse events.   |
| U.4               | Entrance VA (if applicable)                                       | Record the entrance distance visual acuity (OD, OS) to the nearest letter.  |
| U.5               | Subjective Sphero-cylindrical Refraction (if applicable)          | Perform bare-eye subjective sphero-cylindrical refraction with a phoropter (adopt the maximum plus to maximum visual acuity (MPMVA) approach and use the duo-chrome test for binocular balancing) and record the best corrected distance visual acuity to the nearest letter (OD, OS). |

**Clinical Study Protocol**  
**Johnson & Johnson Vision Care, Inc.**

| Unscheduled Visit |  |   |  |
|-------------------|--|---|--|
| Step              | Procedure                                  | Details   |  |
| U.6               | Slit Lamp
Biomicroscopy (if applicable) | FDA Slit Lamp Classification Scale will be used to grade the findings. If the clearance of the fluorescein needs to be expedited, preservative-free rewetting drops may be instilled.             |  |
| U.7               | Dispensing (if applicable)                 | If the subject requires additional lenses to complete the wear period and is eligible to do so, provide additional lenses per the dispensing instructions given in the detailed study procedures. |  |
| U.8               | Exit Visual Acuity (if applicable)         | Record the subject's exit distance visual acuity (OD, OS) to the nearest letter.  |  |

**Note:** If the only reason for the unscheduled visit is that the subject requires additional test articles, only the dispensing information needs to be recorded.

#### **7.4. Laboratory Procedures**

None

### **8. SUBJECTS COMPLETION/WITHDRAWAL**

#### **8.1. Completion Criteria**

Subjects are considered to have completed the study if they:

- provide informed consent,
- are eligible to participate the study, and
- completed all study visits.

#### **8.2. Withdrawal/Discontinuation from the Study**

A subject will be withdrawn from the study for any of the following reasons:

- Subject death during the study period.
- Subject withdrawal of consent.
- Subject not compliant to protocol.
- Subject lost to follow-up.
- Subject no longer meets eligibility criteria (e.g. the subject becomes pregnant).
- Subject develops significant or serious adverse events causing discontinuation of study lens wear.
- Subjects who have experienced a Corneal Infiltrative Event (CIE).
- Investigator's clinical judgment regarding the subject safety reasons (that it is in the best interest of the subject to stop treatment).
- Subject missed any scheduled study visits.
- Subject not compliant with study lens wear schedule.

